## **5.2     Breaking the Blind**

The randomization can be broken, if necessary per the physicians caring for the subject to ensure subject safety.

## **5.3     Drug Supplies**

### **5.3.1     *Formulation, Preparation and Dispensing***

Melatonin 0.5 mgs in a fast dissolve tablet manufactured by Natrol®, LLC ([name]) will be dispensed by study staff to participants. The manufacturer is providing the melatonin for this study free of charge. They will be provided with a 14-day supply at the start of the study and at the first follow-up treatment visit (week 1).

### **5.3.2     *Drug Storage and Drug Accountability***

Melatonin will be stored in the Sleep and Circadian Research Laboratory in a locked cabinet, to which only study staff will have access. Melatonin will be provided by study staff to participants in bottles equipped with a TrackCap to monitor the date and time at which the bottle was opened. Reconciliation of medication will be tracked at each study visit by pill count completed by study staff and by download of the TrackCap data at each study visit.

## **5.4     Concomitant medications**

Medications that may interact with melatonin will not be allowed during the study (list of possible interactions obtained from the Food, Herbs, and Supplements Database available at <https://naturalmedicines.therapeuticresearch.com>). Participants enrolled in the study will not be allowed to take alcohol, nifedipine, anti-hypertensive medications (including, but not limited to, chlortalidone, chlorothiazide, hydrochlorothiazide, indapamide, metolazone, lisinopril, benazepril, captopril, candesartan, losartan, amlodipine, diltiazem); immunosuppressants (including, but not limited to, prednisone, budenoside, prednisolone, cyclosporine, tacrolimus, sirolimus, everolimus, azathioprine, leflunomide, mycophenolate); sedative or hypnotic medications (including, but not limited to, zolpidem, suvorexant, butabarbital, quazepam, estazolam, flurazepam, triazolam, eszopiclone, temazepam, secobarbital, doxepin, zaleplon); antidiabetes drugs (including, but not limited to, metformin, glyburide, glipizide, glimepiride, repaglinide, nateglinide, rosiglitazone, pioglitazone, canagliflozin, dapagliflozin, liraglutide); anticoagulant/antiplatelet (including, but not limited to, heparin, warfarin, rivaroxaban, dabigatran, apixaban, edoxaban, enoxaparin, fondaparinux, clopidogrel, ticagrelor, prasugrel, dipyridamole, dipyridamole/aspirin, ticlodipine, eptifibatide); CYP4501A2 strong or moderate inhibitors or inducers (including, but not limited to, fluoroquinolones such as ciprofloxacin, fluvoxamine,

verapamil, St. John's wort, modafinil, nafcillin, omeprazole). If they require one of the medications on this list, they will be discontinued from the study.

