### **6.2 Treatment Study Period**

#### **Visit 1 (Day 1)**

Participants will have their first session with the study clinician at Visit 1. Prior to the session, study staff will meet with the participant to download their actigraphy. Study staff will provide the study clinician with the initial clock time at which each participant should take melatonin. The initial clock time of melatonin administration for participants assigned to the M-DLMO condition will be set at 3 h before their measured baseline DLMO. The initial clock time of melatonin administration for participants assigned to the E-DLMO condition will be set at 5 h before their average time of sleep onset at baseline per most recent 7 days of actigraphy. Participants be provided with a 14-day supply of melatonin 0.5 mgs, which they will begin taking that evening.

During the first visit, study staff will query whether participants have had any changes in their medications or medical history since the screening, and review concomitant medications. Participants' baseline sleep diary and actigraphy data will be reviewed by the study clinician. The study clinician will provide them with specific instructions regarding when to take melatonin, their bed time, their wake time, and when to dim ambient lighting and electronic devices to their lowest usable level (timed to be approximately 60 minutes before their scheduled bedtime). They will be provided with a handout summarizing this information.

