## 7.1 Primary Endpoint Assessments

Protocol activity and assessments are summarized in Table 1 above.

Primary endpoint: change in the time of DLMO from pre- to post-treatment.

To assess time of DLMO, all eligible participants (regardless of group assignment) will undergo in-home salivary DLMO collection at pre- and post-treatment, using the protocol established by [name] (Co-I) ([name] et al. 2015). Participants will be oriented to the collection procedures during their clinic visit. Participants will be in dim light starting 30 minutes prior to the first sample collection. Collection begins 6 hours prior to participants' habitual sleep onset per their most recent week of actigraphy at baseline. At post-treatment, collection begins 6 hours prior to participants' bed time as assigned at the final treatment session. Samples are collected via Salivette every 30 minutes until bedtime (13 samples total). They are provided with a kit, which includes: a checklist of procedures; a test tube rack; a toothbrush; a nightlight; blue-blocking Uvex glasses (with an Actiwatch attached to monitor compliance of use); an iPod programmed to alarm at collection times; a light medallion (an Actiwatch with light sensor worn around the neck to monitor compliance with light exposure); Salivette collection vials equipped with Track Cap, which will record when the vial was opened; and a label dispenser with pre-labeled labels. Participants wear the blue-blocking glasses throughout the dim light saliva collection and are required to remain seated in the 10 minutes before each sample. When the iPod alarms, participants brush their teeth without toothpaste, collect saliva by chewing on the Salivette, and deposit it in the vial. Participants are informed about the compliance measures utilized in the study. Samples will be stored in participants' freezers until they can be transported to our facility. Samples are centrifuged for two minutes, frozen, and assayed using Bühlmann Laboratory radioimmunoassay (ALPCO Diagnostics, Salem, NH) at **Solidphase Inc.** To ensure consistency and to minimize the effects of sleep schedule changes on the weekends/days off of work, whenever possible, all participants will complete DLMO collection on the third night of their typical workday sleep schedule (e.g., DLMO collection will occur on a Wednesday, Thursday, or Friday night for participants who work a traditional Monday-Friday schedule).

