**Table 2. Study-Specific AE Reporting Timeline**

Reportable Events	Timing of Report to IRB and FDA
Unanticipated problem involving risks to subjects or others related to this research study	Serious: within 7 days Non-serious: with scheduled continuing review
Any physical, social, or psychological harm attributable to participation in this research study (e.g., an injury occurring during a study visit, infection at the site of a blood draw if antibiotics are required)	Serious: within 7 days Non-serious: with scheduled continuing review
Death while on study regardless of relatedness	Within 7 days
Privacy violation or breach of confidentiality	Within 7 days
Protocol deviations not related to an adverse event	With scheduled continuing review
Unanticipated problem related to the research that is not a serious adverse event	With scheduled continuing review
Expected, minor side effects commonly associated with melatonin use: 

• Dizziness

• Sleepiness

• Headache

• Nausea

• Transient depression

• Insomnia

• Nightmares or vivid dreams

• Diarrhea

• Irritability

	With scheduled continuing review
Other serious events not attributable to the research except death as noted above	With scheduled continuing review

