## **9. DATA ANALYSIS/STATISTICAL METHODS**

### **9.1 Sample Size Determination**

We based our sample size estimation on the number of participants necessary to detect a 1 h change in DLMO; the sample size required to detect this change at 90% power with an alpha of 0.05 is 23 per group. Thus, our proposed sample of 25 participants per group (50 total) should be adequate to detect a clinically meaningful change in DLMO.

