#### ***9.2.1 Analysis of Primary Endpoint***

Change in DLMO from pre- to post-treatment will be calculated in minutes for each participant. A 2-tailed t-test will evaluate the difference between the change in DLMO between the two groups.

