#### ***12.4.2 Rules for Discontinuation of a Subject***

In the event a patient drops out of the study or is discontinued due to protocol violations, all attempts will be made to exit the patient in accordance with the protocol requirements.

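### Needing a listed medicine ends study participation, not only melatonin, so a randomised participant's post-treatment DLMO is lost by default; the likely effect is small and the remedy is cheap

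*Combined protocol and SAP*

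**What the plan says.** Section 5.4 lists medicines not allowed during the study and closes with the rule "If they require one of the medications on this list, they will be discontinued from the study". The list includes "sedative or hypnotic medications (including, but not limited to, zolpidem, suvorexant" and others, modafinil, and several classes with no obvious link to sleep, such as antihypertensives and anticoagulants.

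Table 1 puts randomisation at Screen/Baseline. Medication changes are checked after that: at Visit 1 "study staff will query whether participants have had any changes in their medications or medical history since the screening", and section 6.2.1 repeats the check at every follow-up session.

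On the primary outcome, section 7.1 says that all eligible participants "will undergo in-home salivary DLMO collection at pre- and post-treatment". Table 1 places the two collections at Screen/Baseline and Follow-up 4 and has no early-termination column. Section 9.2.1 gives the analysis: "A 2-tailed t-test will evaluate the difference between the change in DLMO between the two groups".

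For dropouts and participants discontinued for protocol violations, section 12.4.2 says "all attempts will be made to exit the patient in accordance with the protocol requirements". No section defines what an exit requires. Section 9 names no analysis set, intention-to-treat rule or missing-data method. The sensitivity analyses in section 5.1 concern only participants whose DLMO cannot be determined.

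**The concern.** Leaving treatment and leaving the study are different events, and section 5.4 merges them. A participant who stops melatonin could still give the second saliva profile. One who has left the study would not, and a test on change scores then omits that person.

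Two things are at stake. First, the comparison is no longer between the groups as randomised. The omission may also be informative: sedative-hypnotics and modafinil act on the very symptoms that define the disorder, and Table 2 names insomnia and sleepiness among the "Expected, minor side effects commonly associated with melatonin use". A participant who is responding poorly could be the one who needs such a drug, and dosing time is what was randomised. Second, the planned sample has little room for loss from any cause, and this source is avoidable.

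**Working it through.** **Does the plan as written lose the outcome?** Taking the sections in order: 5.4 ends study participation; Table 1 and 7.1 schedule the second DLMO only at Follow-up 4; 12.4.2 promises an orderly exit but names no DLMO; 9.2.1 needs both values. No other section restores the missing value. Loss is the default reading, not an explicit instruction.

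**Reproducing the sample size.** Section 9.1 gives a 60 min difference, alpha 0.05, 90% power and 23 per group, with 25 planned. Section 9.2.1 makes the test two-sided. No SD is stated, so the figure cannot be reproduced from the documents' inputs alone. Solving the two-sample t-test (noncentral t) backwards:

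- The largest SD for which 23 per group gives 90% power is 61.4 min.
- With SD 60 min, the required size is 22.02, which rounds up to 23.

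Both are compatible with 23, so both are carried forward.

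**Power under loss.** The rate of new need for a listed medicine is not given. Assume 2% to 10%:

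- 25 × 0.02 = 0.5 lost per arm, leaving 24.5 on average
- 25 × 0.10 = 2.5 lost per arm, leaving 22.5 on average

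| Analysed per arm | Power, SD 60 min | Power, SD 61.4 min |
|---|---|---|
| 25 | 93.4% | 92.3% |
| 24.5 | 92.9% | 91.8% |
| 23 | 91.3% | 90.0% |
| 22.5 | 90.6% | 89.3% |

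The assumed range costs about 0.5 to 3 percentage points. The margin from 23 to 25 is 2 per group, or 2/25 = 8%, for all causes together.

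**Bias.** Let a fraction f of one arm be lost, and let D be the mean advance of those retained minus the mean advance of those lost. The full-arm mean is (1 − f) × retained + f × lost, so the retained mean differs from it by f × D. With f = 0.10 in one arm only and D = 60 min (both assumed), the bias is 0.10 × 60 = 6 min, one tenth of the 60 min target. With f = 0.02 it is 0.02 × 60 = 1.2 min. Loss of poor responders from M-DLMO would inflate its apparent benefit; the same loss from E-DLMO would shrink it. If f and D are equal in both arms, the bias cancels.

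**The case against.** The strongest reply is that very few people will be affected. Exclusion criterion 6 in section 4.1.2 already removes current users of these drug classes, and treatment lasts 28 days. Section 6.2.1 lets the clinician adjust melatonin time or time in bed, which may reduce the need for a sleep medicine. Both arms take the same dose, and participants and the study clinician are blinded to assignment. All of this stands, and it keeps the point modest.

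A reader might infer that the rule removes treatment failures and so favours one arm. The documents do not support that. No section describes a hypnotic being started because the timing failed, the link to response is weak for antihypertensives, antidiabetes drugs and anticoagulants, and nothing points to unequal loss.

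A reader might also count alcohol, which section 5.4 forbids, as a trigger. The rule concerns medications that a participant requires, which does not clearly reach alcohol, and the point does not need it.

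Section 12.4.2 could be read as allowing exit assessments, so it does not show that outcomes are abandoned. But it covers dropouts and protocol violations and names no DLMO, so it does not secure one either. The weekly actigraphy and diary data already collected can still enter the secondary mixed models; that does not help the primary endpoint.

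Finally, invalid saliva profiles may matter more. Section 1.2 cites 83% valid in-home samples in this disorder. If that applied per participant at one assessment (an assumption), 25 × 0.83 = 20.75 per arm would remain, with power of about 87-88%. This is a reason not to add avoidable loss. It does not answer the point about section 5.4.

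**Conclusion.** The point holds as a cheap improvement worth making, not as a serious threat to the trial. As written, sections 5.4, 7.1, 9.2.1 and 12.4.2 together drop from the primary comparison any randomised participant who comes to need a listed medicine, and nothing in section 9 deals with it.

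The size is small under the stated assumptions: at 2-10% loss, power is 89% to 93% instead of 92% to 93%, and a one-sided 10% loss with a 1 h poorer response biases the contrast by 6 min. The loss rate, the one-sided pattern and the 1 h difference are all assumptions, and the SD is inferred.

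It would go too far to conclude that this rule alone breaks the stated 90% power. Section 9.1 holds that "our proposed sample of 25 participants per group (50 total) should be adequate"; with SD 60 min, power stays at 90.6% even at the top of the assumed range, and with SD 61.4 min it falls only to 89.3%.

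**What to change.** Leave the clinical rule on listed medicines and melatonin unchanged. Then:

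1. State in 5.4 and 12.4.2 that discontinuing study treatment does not end follow-up. With the participant's consent, seek the post-treatment DLMO, actigraphy and questionnaires at the scheduled final time point.
2. Add a timing anchor in 7.1. Post-treatment saliva collection is currently tied to the bedtime assigned at the final treatment session, which an early stopper may not have. Start 6 h before the last assigned bedtime in that case.
3. State in 9.2.1 that participants are analysed in their assigned arm whether or not they stopped melatonin.
4. Add a sensitivity analysis that excludes DLMO profiles collected while taking a medicine listed in 5.4 or one named in exclusion criterion 11 of 4.1.2 as interfering with melatonin measurement (daily NSAIDs, beta-blockers).

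The cost is mainly wording, because section 7.1 already plans the second collection for every participant; the documents contain no budget against which to check this. The downside is that some DLMOs will be measured off treatment, so the primary contrast becomes the effect of the assigned timing method whether or not melatonin was continued. The sensitivity analysis shows how far profiles taken under these medicines influence the result.

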## **6 STUDY PROCEDURES**

### **6.1 Screening Visit**

Potential participants will be screened for initial eligibility using an in-person diagnostic interview, including the Mini-International Neuropsychiatric Interview (M.I.N.I) and a sleep interview. In order to maintain the integrity of the data, participants screening visits will not be scheduled around the start or end of daylight savings time.

During second level screening, participants will complete health history and demographic forms (including current and past medical history, and current medications) and female participants of childbearing potential will complete a urine pregnancy test. Participants who meet eligibility criteria following completion of the forms and pregnancy screen will maintain self-selected sleep-wake schedules at home for approximately 7-14 days with daily sleep-wake diaries and actigraphy monitoring to evaluate study criteria for DSWPD and determine full eligibility.

Participants who are eligible for the study following full screening will complete baseline study questionnaires and complete an orientation to the in-home DLMO collection protocol. Participants who do not meet eligibility criteria will be provided referrals for clinical care through the CSDC or BSM clinics.

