### **2.2.1 Primary Endpoint**

The primary endpoint is change in time of DLMO from pre- to post-treatment.

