## 7 ASSESSMENTS

**Table 1. Protocol Activity by Visit**

Protocol Activity	Screen/ Baseline	Visit 1	Follow-up 1	Follow-up 2	Follow-up 3	Follow-up 4 (Final)
		Day 1	Day 7 $\pm$ 5 business days	Day 14 $\pm$ 5 business days	Day 21 $\pm$ 5 business days	Day 28 $\pm$ 5 business days
Week (approximate)	0	1	2	3	4	5
Visit #	0	1	2	3	4	5
Informed Consent	X					
Interview and Medical History	X					
Pregnancy Test (females of childbearing potential)	X					
Randomization	X					
DLMO	X					X
Daily sleep diary	X	X	X	X	X	X
Wrist actigraphy	X	X	X	X	X	X

Melatonin Treatment		X	X	X	X	X
Adverse Event Assessment			X	X	X	X
Concomitant Medication Assessment	X	X	X	X	X	X
Daytime functioning and sleep self-report measures	X					X

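### The daylight-saving rule is tied to screening visits and does not protect the interval between the two DLMO collections, which adds avoidable variance to the primary endpoint

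*Combined protocol and SAP*

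**What the plan says.** The only daylight-saving rule is in section 6.1: "screening visits will not be scheduled around the start or end of daylight savings time". The stated reason is data integrity. The number of days that counts as *around* a change is not given.

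Screening is followed by "self-selected sleep-wake schedules at home for approximately 7-14 days with daily sleep-wake diaries and actigraphy monitoring", then the baseline DLMO. Table 1 places the second DLMO at the final visit, Day 28 with a window of 5 business days either side.

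Section 2.2.1: "The primary endpoint is change in time of DLMO from pre- to post-treatment". Section 9.2.1: "Change in DLMO from pre- to post-treatment will be calculated in minutes for each participant", and then "A 2-tailed t-test will evaluate the difference between the change in DLMO between the two groups". No reference clock, conversion, covariate or sensitivity analysis for a clock change appears.

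Two neighbouring safeguards do not reach the problem. The travel exclusion in 4.1.2 concerns trips across more than one time zone. The minimization in 5.1 balances age and free-day sleep onset, not calendar date.

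**The concern.** The endpoint is the difference between two times of day taken several weeks apart. If the clocks change in between and a participant's rhythm does not follow, the change score moves by 60 min with no circadian shift: later in spring, which hides an advance, and earlier in autumn, which mimics one. The trial is sized on the "number of participants necessary to detect a 1 h change in DLMO", so one participant's shift can be as large as that figure.

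The plan recognises the threat but places the safeguard on a date that comes before the interval at risk. People who straddle a change were screened weeks ahead of it, where a short blackout around the change does not reach. At stake are the precision of the primary comparison and, if nothing is pre-specified, a choice after the data are seen about what to do with straddlers.

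**Working it through.** **Inputs from the documents.** 23 per group for 90% power at alpha 0.05 and 1 h; 25 per group planned (9.1). Two-tailed t-test on change scores (9.2.1). Monitoring of 7-14 days after screening (6.1).

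**Assumptions.** Two 60-min clock changes a year; even enrolment; gap D between the two DLMOs of 28-42 days (the lag between the baseline DLMO and Visit 1 is not stated); 1 h read as a between-group difference.

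**1. SD behind the plan's figure.** None is given, so 23 per group can only be back-solved. Normal approximation: SD = 60 × √(23 / (2 × (1.960 + 1.282)²)) = 62.8 min. Noncentral t: 61.4 min. An SD of 60 min also gives 23 by the t-test, so the figure is plausible. With 61.4 min, power at 25 per group is 92.3%.

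**2. Share who straddle a change.** With no blackout the share is 2D/365: 56/365 = 15% at 28 days, 84/365 = 23% at 42 days.

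Now bar screening within B days either side of each change, which leaves 365 − 4B eligible days. With the baseline DLMO m days after screening, straddlers are those screened between m and m + D days before a change. If B ≤ m, none of them is removed and the share is 2D/(365 − 4B). If B > m, it is 2(m + D − B)/(365 − 4B), or zero once B reaches m + D. Averaging over m from 7 to 14 days:

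| B (days) | D = 28 | D = 42 |
|---|---|---|
| 0 | 15% | 23% |
| 7 | 56/337 = 17% | 84/337 = 25% |
| 14 | 49/309 = 16% | 77/309 = 25% |
| 21 | 35/281 = 12% | 63/281 = 22% |
| 35 | 7/225 = 3% | 35/225 = 16% |

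If every baseline DLMO came 14 days after screening, B = 14 gives 56/309 = 18% to 84/309 = 27%. If every one came at 7 days, it gives 42/309 = 14% to 70/309 = 23%. A short blackout mostly removes people who would not have straddled. The working range is about 15-27%, or roughly 8 to 14 of 50.

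**3. Variance and power.** For a share p and a retained shift a, the variance of the change score is 61.4² + p·a² when spring and autumn are equally mixed, and 61.4² + p(1 − p)·a² when all changes go one way.

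| a | p | SD, mixed | Power at 25, mixed | Power at 25, one way |
|---|---|---|---|---|
| 60 min | 0.15 | 65.6 | 88.6% | 89.2% |
| 60 min | 0.27 | 68.8 | 85.5% | 87.4% |
| 30 min | 0.15 | 62.5 | 91.4% | 91.6% |
| 30 min | 0.27 | 63.3 | 90.7% | 91.1% |

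With the full 60 min, 26-29 per group would be needed for 90%.

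**4. Effect on the arm difference.** One extra same-direction straddler in an arm moves it by 60/25 = 2.4 min. The SD of the chance imbalance is √(2·p·60²/25) = 6.6 min at p = 0.15 and 8.8 min at p = 0.27 (mixed), or 6.1 to 7.5 min one way. An imbalance of at least 12 min has probability of about 7-22%; at least 30 min, below 0.1%. In simulations with 25 per arm at p = 0.20 and 0.27, mean bias was about zero and type I error 4.8-5.0%.

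**The case against.** **Unlike quantities.** A reader might infer that a shift equal to the 1 h target could produce or cancel the treatment effect. It cannot. The test compares arms that are equally exposed in expectation, and a 60-min artefact in the difference would need all 25 of one arm and none of the other to straddle in the same direction. This objection stands: the harm is lost precision, not bias.

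**The power loss is a ceiling.** Dose, bed and wake times are set by the clock, and the trial presumes that such scheduling can move DLMO within four weeks, so some re-entrainment is likely. With half the shift retained, power stays above 90%. This stands too. A reader who takes it as settled that power falls below 90% goes further than the documents allow, particularly as the SD is back-solved.

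**A broader reading of the rule.** Section 6.1 speaks of visits in the plural and covers monitoring and orientation to DLMO collection; Table 1 puts the baseline DLMO in the combined screening and baseline column. If the rule bars baseline collection within B days of a change, the share is 2(D − B)/(365 − 4B). At B = 14 that is 28/309 = 9% to 56/309 = 18%; at B = 28 it is zero for a 28-day gap but 28/253 = 11% for 42 days. So even this reading closes the gap only if *around* means four to six weeks, and the text does not say so.

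**Dose timing is not fixed.** Section 6.2.1 moves dose and schedule by 1 h at each weekly session until the desired schedule is reached, with clinician discretion. It would be wrong to say participants stay on one clock time throughout. The documents are nevertheless silent on a clock change during treatment.

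**Conclusion.** The point holds in limited form. Followed as written, the rule in 6.1 does not protect the interval that determines the primary endpoint, and the analysis has nothing to compensate. About 15-27% of participants could straddle a change, each with up to 60 min of non-treatment shift. The consequence is a loss of at most about 3-7 percentage points of power at 25 per arm (92% to 85-89%), about 1-2 points if half the shift is retained, and a chance imbalance between arms with an SD of about 6-9 min at most. Expected bias is about zero and the type I error rate is unaffected.

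These figures rest on even enrolment, the assumed 28-42 day gap, the back-solved SD of 61.4 min, and the reading of the 1 h in 9.1 as a between-group difference. The documents do not support a conclusion that the treatment comparison would be biased. This merits a change because the remedy is cheap and the plan already names the threat, not because the trial's validity depends on it.

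**What to change.** **Section 6.1.** Set the scheduling rule by the DLMO interval: where feasible, no start or end of daylight saving time falls between the baseline and post-treatment collections. Record the clock in force at each collection.

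**Section 9.2.1.** Replace the bare t-test with a linear model of change in DLMO on group and a signed straddle term (+1 spring, 0 none, −1 autumn). Pre-specify a sensitivity analysis without straddlers.

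**Cost.** One degree of freedom (48 to 47 with all 50 evaluable) and some scheduling constraint. The covariate estimates the average retained shift, so it need not assume whether people re-entrain; it does not remove variation in retention between people.

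**What need not be mandatory.** A hard pause in baseline collections of 5-6 weeks twice a year would close about 70/365 = 19% to 84/365 = 23% of the calendar. The pool of at least 95 patients a year in 4.1 makes this conceivable, but that figure counts diagnosed patients before exclusions and consent. Re-expressing both DLMOs on one fixed clock would introduce a 60-min error in anyone who has fully re-entrained, so it should not be the default.

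**To be reconciled.** Sections 6.2 and 6.2.1 set dose and bed-wake times by the clock, and 6.2.1 counts dose-time departures of 30 minutes or more as non-compliant. The protocol should state how those clock times, and the deviation rule, are handled when the clocks change during treatment.
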